Personally Identifiable Information: Access, Management, and Protection The study staff will have access to individually identifiable data about participants. The NH leadership team will have access to individually identifiable data about participants (see also Protection of Human Subjects, section 1.a, sub-sections Subject Populations and Collaborating Sites and Roles). To protect against the risk of accidental access to or inappropriate divulging of identifiable data, the flow of individually identifiable data and steps to assure its appropriate access, management, and protection, are outlined below.

1. NH Residents

a. Study staff will successfully obtain all necessary IRB authorizations for protocols and materials described below

b. NH leadership team or their designees will identify all NH residents with an ADRD diagnosis and the NH leadership team will mail to those residents' legally authorized representatives (LARs) an IRB-approved study introduction letter (including option to opt out within one month if they do not wish to be contacted by study staff). Contact information of those LARs not opting out will be shared with University of Alabama (UA) study staff.

c. UA study staff will contact LARs and attempt to gain informed consent for NH resident participation. Study staff will weekly provide an updated list of consented residents with study identification numbers to the NH leadership team along with copies of all completed informed consent forms so that a copy can be filed in the resident's medical records and a copy can be stored along with the complete list and other IRB approvals and relevant study information in an essential documents binder (electronic or physical) at the NH. These processes will assure that NH staff will be able to easily verify that study staff only have access to personally identifiable data of residents are involved in the study.

d. NH staff will work together in frontline huddles to complete screening of all eligible residents, identify residents with sleep problems to enroll in the LOCK sleep program, and collect assessment data for enrolled residents.

e. Every week, the NH leadership team will use researcher-provided tracked express mail service envelopes to send the UA study staff the following: 1) all completed staff rating forms, identified by NH resident subject number; and 2) any actigraphs and Fitbits for which the assessment periods are complete, identified by subject number. Research staff will mail back actigraphs and Fitbits after data download, deletion of data from the devices, and maintenance.

f. UA study staff will conduct a virtual visit to each NH during the post-intervention period to work with NH staff to extract information from the medical records of consented NH residents.

g. UA study staff will upload all data at UA and then transfer to the University of Texas School of Public Health (UTHealth SPH) Data Center via secure file transfer procedures as established by [name] and the Data Center.

h. MDS data will be obtained by [name] and the UTHealth SPH Data Center through data use agreement for use of personally identifiable information from CMS. MDS data for consented NH residents will be linked and merged with the other data described above.

i. When data are reported in publication and presentation they will only be reported in aggregate form, and neither NH nor participant will be identifiable.

2. NH Staff for interviews

a. Study staff will successfully obtain all necessary IRB authorizations for protocols and materials described below.

b. NH leadership team will provide to all NH staff an IRB-approved study introduction letter (including option to opt out within one month if they do not wish to be contacted by study staff). Contact information of those NH staff not opting out will be shared with UA study staff.

c. UA Study staff will contact NH staff to invite them to participate in mid-implementation virtual interviews. Study staff will also contact NH staff to invite them to participate in post-implementation interviews. The list of NH staff who agree and decline interview participation will remain confidential to protect NH staff from any possible coercion to participate (see 1.3.b. Protection Against Risks).

d. UA study staff will conduct virtual interviews with consented NH staff. Interviews will be audio recorded. Recordings will be uploaded at UA, identified only by subject number, and shared with a university-approved transcription service via secure file transfer procedures as established by [name] and the UTHealth SPH Data Center. Transcribed files, identified only by subject number, will be returned via the same secure file transfer procedures to UA for tracked storage and analysis and to Drs. [name] and [name] at Boston University for analysis.

e. When data are reported in publication and presentation they will only be reported in aggregate form, and neither NH nor participant will be identifiable.

3. Data Management and Protection. [name] and the UTHealth SPH Data Center will create protocols for overseeing the security and protection of all data collected for this study. Personally identifiable information will be only be stored in the secure and securely backed up UA data server and UTHealth SPH Data Center in password protected files. Other collaborating sites (Boston University, Brown University, and University of Texas at Austin) will only work with data identified by subject number.

2.0 Interim Analysis

At the first meeting, the Data Safety and Monitoring Board (DSMB) will decide if an interim analysis will take place (e.g. after n participants have been accrued or completed the trial). Interim analyses of efficacy data will only be performed if planned and approved in advance, and when criteria for possible stopping are clearly defined.

It is not anticipated that interim analyses will be undertaken given the minimal potential risks to participants in this trial.

3.0 Data and Safety Monitoring The DSMB procedures are described above in the Risks Sub-section #8b.

If no, please justify why not.

* * * Benefits/Alternatives, Procedures to Maintain Confidentiality * * *

9. Benefits/Alternatives

a) Benefits. Describe the potential benefit(s) to be gained by the participants and how the results of the study may benefit future participants and/or society in general. Indicate if there is no direct benefit to the participants.

The intervention may benefit NH residents by leading to better and earlier detection and treatment of sleep problems and from increased attention to their conditions. The intervention may benefit NH staff by improving communication and teamwork, thereby improving the work experience.

Sleep problems and related issues in NH residents with dementia is a well-documented problem. This study implements an intervention to improve the sleep experience for these residents and increase access to meaningful activities. If the LOCK sleep program is found to be effective in enhancing clinical care and outcomes, the approach can be shared with other NHs and incorporated into general NH practice. The risks in this study for NH residents are minimal, and the knowledge gained may result in improved quality of sleep, and ultimately improved quality of life for NH residents with dementia. Similarly the risks for NH staff are minimal, and the knowledge to be gained may result in a more effective and enjoyable workplace experience. Thus, the potential benefits exceed risks.

b) Alternatives. Describe any alternative treatments and procedures available to the participants should they choose not to participate in the study. If no such alternatives exist, please state that the alternative is nonparticipation. For some studies, such as record reviews, a description of alternatives would not be applicable.

The intervention described will be implemented NH-wide. The study uses an incomplete stepped-wedge cluster randomized controlled trial design in which each NH serves as its own control. There will therefore be no alternative treatments. NH residents and their legally authorized representatives will have the right to refuse participation in any portion of their care just as they would with usual NH care, including use of actigraphs and Fitbits. NH staff will have the right to refuse any interviews.

10. Procedures to Maintain Confidentiality

Federal regulations require that study data and consent documents be kept for a minimum of three (3) years, and HIPAA documents be kept for a minimum of six (6) years after the completion of the study by the PI. For longitudinal or sponsored projects, the PI may be required to keep the data and documents for a longer time period.

Data Security

Please indicate how information will be secured. All information must be stored using at least two of the following safeguards and must be kept in accordance with the University of Alabama Information Security Policies. (If you are using both electronic data and hard copy data, you will need two safeguards for each type).

- a) Electronic Data: (mark all that apply at least 2 or indicate not applicable) Not applicable
 - X Password access

X Coded, with a master list kept as a hardcopy or on a secure network (confidential) Data collected anonymously Secure network (e.g., firewall)

Data are de-identified by PI or research team

Other

Please specify:

 b) Hardcopy Data: (mark all that apply - at least 2 - or indicate not applicable)) Not applicable

Locked suite

X Locked office

X Locked file cabinet

X Coded, with a master list secured and kept separately (confidential) Data collected anonymously

24 hour personnel supervision

Data are de-identified by PI or research team

Other

Please specify:

c) Describe measures employed to protect the identity of the participants, their responses, and any data that you obtain from private records (e.g., identifiers will be stripped so data cannot be linked to participants, or code numbers will be used, etc.). If data will be coded, specify the procedures for coding the data so that confidentiality of individual participants is protected. If you will keep a master list linking study codes to participant identifiers, explain why this is necessary, how and where you will secure the master list, and how long it will be kept.

Sources of Materials

NH resident data will be collected for consented NH residents from NH staff ratings (global assessments of change in overall sleep quality and sleep-related conditions; Sleep reports from NH staff), NH staff sleep interview of resident, family/friend sleep interview about resident, and actigraph/Fitbit measurements (wristwatch-sized devices worn on the wrist); medical records (age, diagnoses, medical history, and medications); and MDS assessments (Brief Interview for Mental Status score, psychotropic medication use, pain and analgesic medication use, activities of daily living decline, sleep-related items). NH staff interview data will be collected via audiorecorded qualitative interview. See Table 1 in Attachments for a listing of all study outcomes and data sources.

Personally Identifiable Information: Access, Management, and Protection The study staff will have access to individually identifiable data about participants. The NH leadership team will have access to individually identifiable data about participants. The flow of individually identifiable data and steps to assure its appropriate access, management, and protection, are outlined below.

1. NH Residents

a. Study staff will successfully obtain all necessary IRB authorizations for protocols and materials described below

b. NH leadership team or their designees will identify all NH residents with an ADRD diagnosis and the NH leadership team will mail to those residents' legally authorized representatives (LARs) an IRB-approved study introduction letter (including option to opt

representatives (LARs) an IRB-approved study introduction letter (including option to opt out within one month if they do not wish to be contacted by study staff). Contact information of those LARs not opting out will be shared with University of Alabama (UA) study staff.

c. UA study staff will contact LARs and attempt to gain informed consent for NH resident participation (see 2.a. Informed Consent and Assent). Study staff will weekly provide an updated list of consented residents with study identification numbers to the NH leadership team along with copies of all completed informed consent forms so that a copy can be filed in the resident's medical records and a copy can be stored along with the complete list and other IRB approvals and relevant study information in an essential documents binder (electronic or physical) at the NH. These processes will assure that NH staff will be able to easily verify that study staff only have access to personally identifiable data of residents are involved in the study.

d. NH staff will work together in frontline huddles to complete screening of all eligible residents, identify residents with sleep problems to enroll in the LOCK sleep program, and collect assessment data for enrolled residents.

e. Every week, the NH leadership team will use researcher-provided tracked express mail service envelopes to send the UA study staff the following: 1) all completed staff rating forms, identified by NH resident subject number; and 2) any actigraphs and Fitbits for which the assessment periods are complete, identified by subject number. Research staff will mail back actigraphs and Fitbits after data download, deletion of data from the devices, and maintenance.

f. UA study staff will conduct a virtual visit to each NH once during the post-intervention period to work with NH staff to extract information from the medical records of consented NH residents (this process and the information to be extracted will be clearly described in IRB-approved protocols and consent forms).

g. UA study staff will upload all data at UA and then transfer to the University of Texas School of Public Health (UTHealth SPH) Data Center via secure file transfer procedures as established by [name] and the Data Center.

h. MDS data will be obtained by [name] and the UTHealth SPH Data Center through data use agreement for use of personally identifiable information from CMS. MDS data for consented NH residents will be linked and merged with the other data described above.

i. When data are reported in publication and presentation they will only be reported in aggregate form, and neither NH nor participant will be identifiable.

2. NH Staff for interviews

a. Study staff will successfully obtain all necessary IRB authorizations for protocols and materials described below.

b. NH leadership team will provide to all NH staff an IRB-approved study introduction letter (including option to opt out within one month if they do not wish to be contacted by study staff). Contact information of those NH staff not opting out will be shared with UA study staff.

c. UA Study staff will contact NH staff to invite them to participate in mid-implementation virtual interviews. Study staff will also contact NH staff to invite them to participate in post-implementation virtual interviews. The list of NH staff who agree and decline interview participation will remain confidential to protect NH staff from any possible

coercion to participate.

d. UA study staff will conduct interviews with consented NH staff. Interviews will be audio recorded. Recordings will be uploaded at UA, identified only by subject number, and shared with a university-approved transcription service via secure file transfer procedures as established by [name] and the UTHealth SPH Data Center. Transcribed files, identified only by subject number, will be returned via the same secure file transfer procedures to UA for tracked storage and analysis and to [name] at UMass Lowell for analysis.

e. When data are reported in publication and presentation they will only be reported in aggregate form, and neither NH nor participant will be identifiable.

3. Data Management and Protection. [name] and the UTHealth SPH Data Center will create protocols for overseeing the security and protection of all data collected for this study. Personally identifiable information will be only be stored in the secure and securely backed up UA data server and UTHealth SPH Data Center in password protected files. Other collaborating sites (UMass Lowell, Brown University, and University of Texas at Austin) will only work with data identified by subject number.

d) If data or specimens are being shared outside of the research team, indicate who will receive the material and specifically what they will receive (data or specimens).
N/A. Data will be shared across different sites that are all part of the research team -- this

is described above.

e) If samples or data will be provided from an outside source, indicate whether you will have access to identifiers, and, if so, how identifiable information is protected. Please provide a letter from the appropriate persons indicating that data will be provided in a de-identified manner.

Data will be collected from NH medical records and from NH Minimum Data Set (MDS) records. We will have access to identifiers, and are submitting the appropriate HIPPAA authorizations. We will protect data by separating identifiers from the data itself using subject IDs and a master coding checklist kept locked in a separate location.

f) If data will be collected via e-mail or the internet, how will anonymity or confidentiality be protected? Describe how data will be protected during electronic transmission and how data will be recorded (i.e., will internet protocol (IP) address and/or e-mail addresses be removed from data?).

g) If you will be audio/video recording or photographing participants, provide a rationale for recording/photographing. Describe confidentiality procedures, including the final disposition of the recordings/photos (destruction, archiving, etc.) and a reasonable timeline by which this disposition will occur.

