a) Provide a brief lay summary of the project in <200 words. The lay summary should be readily understandable to the general public.

This study will improve clinical outcomes for an important, growing, and vulnerable population—nursing home (NH) residents with Alzheimer's disease or related dementias (ADRDs)—by implementing an evidence-based intervention (LOCK) to improve these residents' sleep and increase meaningful activity. It will also significantly increase our understanding of how to implement and sustain nursing home interventions.

b) List your research objectives (specific aims & hypotheses of the study).

In community (non-VA) NHs [one from each of 3 NH corporations, still to be recruited], our multi-disciplinary team proposes to (1) refine the LOCK sleep program to improve sleep and increase meaningful activity for residents with ADRD during this pilot (R61) phase, (2) which will prepare the team for the next phase of this NIH-funded grant (the R33 phase, to be described in a follow-up IRB protocol when this phase is completed, in approximately one year) to test the impact and sustainability of this intervention for NH residents with ADRD in an incomplete stepped-wedge randomized controlled trial.

(This study is funded by a National Institute of Aging pragmatic clinical trial RFA and grant mechanism called R61/R33, in which the R61 is a pilot grant for one year. The investigator team submits a report after the R61 phase indicating what was learned during the pilot phase and showing evidence that the pilot milestones are achieved. Then NIA funds the next four years of the randomized controlled trial

with the R33 mechanism. The current proposal only describes the pilot study (R61 phase). A separate proposal will be submitted for the randomized controlled trial (R33) when the R61 phase is close to completion. We will wait to submit the R33 proposal because National Institute of Aging wishes for modifications to the R33 design and intervention to be made based on the R61 data collection/intervention experience and the R61 quantitative and qualitative data analyses.)

This current pilot study R61 phase (1 year; n = 3 NHs; 1 NH per corporation) has the following specific aims:

1. Refine the LOCK sleep program train-the-trainer protocol by implementing and pilot-testing in three NHs.

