2. Test and refine the research methods to: effectively identify eligible NHs and residents; obtain consent; collect primary data from residents and staff; explore staff impressions of additional sleep measurement devices (Fitbits); transfer primary and secondary data to our data center; and merge all data.

c) Describe the study design (e.g., single/double blind, parallel, crossover, control, experimental, observational, etc.)

N/A

Single blind

Double blind

Parallel

Crossover

Control group

Experimental group

Observational

X Other

This is a pilot study (R61 phase) to pilot the methods for an upcoming randomized controlled trial (see study funding mechanism explanation in previous section #2B above). The upcoming randomized controlled trial will be an incomplete stepped-wedge, cluster randomized controlled trial (RCT) design in which each nursing home (NH) serves as its own control. Our design can be classified in the NIH Model for Behavioral Intervention Development as Stage III, real world-based hybrid efficacy-effectiveness research.

This pilot study (R61 phase) pilots the methods for this design in 3 NHs. In this pilot we will use a convenience sample of three nursing homes (NHs), one recruited from each of three different NH corporations that are anticipated to participate in the eventual randomized controlled trial.

Each nursing home will serve as its own control. Control data will be collected for 1 week, then the intervention will begin and intervention data will be collected for 6 weeks, then the sustainment phase will begin and sustainment data will be collected for 8 weeks.

d) Provide a timeline for individual participant recruitment and follow-up (analysis for the study is required).

Each site will serve as its own control.

Control data will be collected for 1 week, then the intervention will begin and intervention data will be collected for 6 weeks, then the sustainment phase will begin and sustainment data will be collected for 8 weeks for a total of 15 weeks per participant.

The duration of the intervention period for any NH is 15 weeks, which includes three 7-day sleep measurement periods (baseline measurement before week 1, post-intervention measurement at week 8, and sustainment measurement at week 15).

e) Will participant be randomized?

Ν

Ν

f) If participants will be given placebo, please justify placebo use, and describe contents of the placebo.
 N/A

3) Study Procedures

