- 7. For clinical studies (of a drug, vaccine, device or treatment), describe any alternative procedure(s) or course(s) of treatment. List important risks and benefits of these alternatives in order to compare to study procedure(s) or course(s) of treatment. This information MUST be included here. Any standard treatment that is being withheld must be disclosed and the information must be included in the consent form.

The intervention described will be implemented NH-wide. The study is a pilot (R61) for the methods for a subsequent randomized controlled trial (R33 -- an incomplete stepped-wedge cluster randomized controlled trial design in which each NH serves as its own control). There will therefore be no alternative treatments. NH residents and their legally authorized representatives will have the right to refuse participation in any portion of their care just as they would with usual NH care, including use of actigraphs and Fitbits. NH staff will have the right to refuse any interviews.

8a. Describe any other physical, psychological, social or legal risks the participant may experience.

No more than minimal risk.

The risks for participants in this trial are minimal. There are no anticipated physical or economic risks associated with this study. There are no psychological risks beyond what was described in Risks sub-item #5 above.

For both NH residents and staff, an unlikely legal or social risk associated with participating in this study would be invasion of privacy in the remote chance that there is a loss or lack of protection of data containing personally identifiable information. These are research risks, not therapeutic risks. The study team will use careful procedures to guard the security and confidentiality of all data.

For both NH residents and staff, a potential risk is that a person may not want to participate in the study and may feel coerced to do so. Therefore, to minimize this type of risk, all informed consent contact with potential participants will come through the study staff only, and all NH staff participation discussions and decisions will be kept confidential.

8b. Data Safety Monitoring

Is there a Data Monitoring Committee (DMC) or Board (DSMB)?

If yes, describe its role, if it is independent of the sponsor or research team, the make-up of the Board and their qualifications, and how often the Board will meet.

1 Frequency of Data and Safety Monitoring

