During a phone appointment, study staff will review all important elements of the ICF with the LAR, including the following: description of the study, information on how to contact the investigators and the NH administrator and director of nursing, a statement that there is no prejudice for refusal to participate, a statement that the subject may withdraw from the study at any time without prejudice, and statement regarding risk and benefit of participation. The LAR will be encouraged to ask questions. The LAR will be encouraged to call the PI if they have any remaining questions before signing the consent form.

NH Resident Consent:

Step 2. Screening for Capacity for NH Resident Consent/NH Resident Assent Some NH residents with mild ADRD and available LARs may have the capacity to provide their own consent. A conservative two-step process will be used to address the ethical balance of the beneficence of assuring that residents who do not have the capacity to consent are protected by LAR oversight with the promotion of autonomy for residents who do have capacity to consent. Once LAR consent is received for a resident, the NH leadership team will be asked to identify that resident's most recent MDS Brief Interview for Mental Status [120] (BIMS; see Appendix for copy of measure) score, a cognitive screening measure with good reliability and validity. For residents with BIMS scores in the mild range (above 10), the NH leadership team will be asked to arrange and support a telephone appointment between that resident and a study staff person (if the resident turns out to not have the cognitive ability to participate in the following telephone-based procedure, then they would also not have the cognitive capacity to provide informed consent, which requires higher level cognitive abilities).

In the telephone appointment, the study staff member will provide information about the study and will screen for capacity to consent by assessing the following. Does the resident respond appropriately to a social greeting? Is the resident oriented to place? Does the resident understand who the study team member is after the team member explains their identity? During the course of this introductory conversation, was the resident able to respond fluently and socially appropriately? If so, the team member will go through the consent form with them. Residents will then be asked a series of questions to assure their understanding. These questions are as follows:

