The study staff member will review with the NH staff member all relevant elements of consent on the consent information sheet, including the following: description of the study activities, time requirement, information on how to contact the investigators, a statement that there is no prejudice for refusal to participate, a statement that the subject may withdraw from the study at any time without prejudice, a statement encouraging the reader to ask questions, and a statement regarding risk and benefit of participation. All informed consent guidelines of the IRB will be followed. If at any time during the interview the staff member indicates a desire to stop participating, the participant will be withdrawn from the interview portion of the study. Confidentiality of all interview data will be protected by using participant code numbers on the data collection forms.

SELECTED REFERENCES

2) Explain how risks, benefits, and alternatives will be discussed.

Risks will be described first. Efforts to mitigate risk (e.g., data security procedures to ensure confidentiality of data, procedures to keep employee participation information confidential, staff training to ensure that cognitively impaired individuals' autonomy and potential withdrawal of assent are honored).

Benefits will then be described in an appropriately tentative manner, as follows. Sleep problems and related issues in NH residents with dementia is a well-documented problem. This study implements an intervention which may improve the sleep experience for these residents. If the LOCK sleep program is found to be effective in enhancing for these residents. If the LOCK sleep program is found to be effective in enhancing clinical care and outcomes, the approach could be shared with other NHs and incorporated into general NH practice. The risks in this study for NH residents are considered minimal, but risk cannot be eliminated. The knowledge gained may result in improved quality of sleep, and ultimately improved quality of life for NH residents with dementia, but benefits cannot be guaranteed. Similarly the risks for NH staff are minimal, but risk cannot be guaranteed to be gained may result in a more effective and enjoyable workplace experience, but these benefits cannot be guaranteed.

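### Section 7(f) commits the pilot to comparing intervention effects by sex, race and ethnicity, which an unrandomized three-home before-after study cannot identify and section 3(d) does not plan; sections 9(b) and 12 also give the pilot the later trial's design

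*Combined protocol and SAP*

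**What the plan says.** **Scope and design.** Section 2(b) states: "The current proposal only describes the pilot study (R61 phase"; the R33 trial is to have its own submission. Section 2(c) separates the phases: "The upcoming randomized controlled trial will be an incomplete stepped-wedge, cluster randomized controlled trial (RCT) design", whereas for the present study "In this pilot we will use a convenience sample of three nursing homes (NHs". The sequence in each home is before-after: "Control data will be collected for 1 week, then the intervention will begin", with six weeks of intervention and eight of sustainment. Actigraphs are worn for three 7-day periods, one before the intervention and two after it starts. Section 3(b), on intervention training and implementation, has the three homes start at roughly the same time.

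**Subgroup commitment.** Section 7(f), on inclusion of women and minorities, undertakes to estimate intervention effects and compare them between sexes and racial or ethnic groups. It calls the analyses unbiased and the inference proper. It adds exploratory analyses to look for differences in effect among these groups.

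**Analysis plan.** Section 3(d) is the only quantitative analysis section. It plans ranges, change over time, missing-data rates, and associations of the secondary and supplementary measures with total sleep time. It also plans a look at the indicators by demographic characteristics, with age and gender as examples, and by dementia severity. It names no effect estimate, model, test or interaction, and does not mention race or ethnicity.

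**Design label.** Section 9(b) and section 12 item 2 both say: "The study uses an incomplete stepped-wedge cluster randomized controlled trial design in which each NH serves as its own control". Section 8(a) item 7 has nearly the same paragraph, but reads: "The study is a pilot (R61) for the methods for a subsequent randomized controlled trial".

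**The concern.** Section 7(f) promises something neither the design nor the analysis section supports. The pilot has no randomization and no concurrent control home, so everything that changes over the 15 weeks is mixed with the intervention. Regression to the mean is a live possibility, because section 3(b) has staff focus on the residents with the greatest sleep problems. Anyone following section 7(f) as written could report that women changed more than men, or one racial group more than another, and call it a difference in intervention effect. Section 2(b) says the pilot's results will shape the R33, so such a reading could carry forward.

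The design label in sections 9(b) and 12 is a smaller matter, but it points the same way. It describes the pilot as the kind of study in which effect comparisons would be legitimate. The section 12 sentence answers an item that asks the investigator to "Explain how risks, benefits, and alternatives will be discussed", so it also bears on what is said at consent.

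**Working it through.** **1. What a subgroup contrast would estimate.** Write the mean pre-post change in group g as

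change(g) = effect(g) + time trend(g) + regression to the mean(g).

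The difference between groups 1 and 2 is then

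[effect(1) − effect(2)] + [trend(1) − trend(2)] + [RTM(1) − RTM(2)].

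Only the first bracket is a difference in intervention effect. The other two vanish only if trend and regression to the mean are the same in both groups, or happen to offset each other. A concurrent control or staggered starts would help to separate trend from effect; the pilot has neither. Checking for different prior trends needs at least two pre-intervention measurements, and actigraph total sleep time has one.

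**2. The plan's own sample figure.** Section 3(b): about 19 residents in each of 3 homes, 19 × 3 = 57. This reproduces. The plan gives no alpha, power, SD or intraclass correlation for the pilot, so there is no precision figure to reproduce.

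**3. Expected group sizes.** These use the percentages in section 7(f): a sex target of 67/33, and national figures of 79% White, 13.8% Black and 4.9% Hispanic.

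| Group | 57 residents | 70 consented (section 7(b)) |
|---|---|---|
| Women / men | 38.2 / 18.8 | 46.9 / 23.1 |
| White | 45.0 | 55.3 |
| Black | 7.9 | 9.7 |
| Hispanic | 2.8 | 3.4 |

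Actual counts may differ. Section 7(f) intends active recruitment of minority members, and the homes are in Colorado, South Carolina and Texas.

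**4. Precision, in SDs of the change score.** SE = √(1/n1 + 1/n2); 95% half-width = t(0.975, n1 + n2 − 2) × SE.

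- Women vs men, 38 vs 19: SE = √(1/38 + 1/19) = 0.281; 2.004 × 0.281 = 0.56.
- White vs Black, 45 vs 8: SE = √(1/45 + 1/8) = 0.384; 2.008 × 0.384 = 0.77.
- With all 70 consented residents (47 vs 23; 55 vs 10): 0.51 and 0.69.
- If the Black share were 5%, 20% or 30% (assumed; 50 vs 3, 41 vs 11, 36 vs 17): 1.19, 0.68 and 0.59.

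These assume independent residents and no missing data.

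**5. Illustration of bias.** Suppose trend plus regression to the mean differs between women and men by d SD of change. The documents give no value, so d is purely assumed. The contrast is then off by d at any sample size. With SE 0.281 and 55 degrees of freedom, the noncentral t distribution says a nominal 95% interval misses the true difference in effect 6%, 14% and 42% of the time for d = 0.1, 0.25 and 0.5. The conclusion does not depend on these figures.

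**6. The design label.** A stepped wedge needs staggered starts and, here, a randomized order of homes. Section 3(b) has a common start, section 2(c) a convenience sample, and sections 2(b), 2(c) and 8(a) item 7 assign the randomized trial to the later phase. The own-control property and the absence of alternative treatments, stated alongside the label, do hold for the pilot. Only the stepped-wedge randomized part is wrong.

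**The case against.** The strongest reply is that section 3(d) governs the analysis and is already modest. It calls the assessment preliminary, plans change over time, and breaks indicators down by demographics. Because age and gender are only examples, race and ethnicity are not excluded. Section 7(f) itself calls the search for differences exploratory. On this view, what remains is the term intervention effect in an inclusion paragraph. Much of this stands: it would be wrong to infer that the plan has no demographic breakdown. But the exploratory label deals with error rates and not with identification, and the claims of unbiased estimation and proper inference remain in current text.

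A reader might also infer that the equal-trend assumption can be checked for no outcome. The documents do not go that far. Section 14 says Minimum Data Set assessments are made at admission, quarterly and at discharge, so earlier records may exist for those secondary outcomes, although the plan does not commit to using them. The point is shown only for actigraph total sleep time.

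On the design label, the same form states the correct design in several places, and no allocation or analysis follows from the wrong sentence. The negative answer in item 2(e) adds little, since that item asks about participants and a cluster trial randomizes homes.

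The tempting stronger reading is that residents or their representatives are told the homes are randomized. The documents do not support it. The consent forms are not in the text, and of the consent call they say that "study staff will review all important elements of the ICF with the LAR, including the following: description of the study", without saying how the design is described.

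**Conclusion.** The concern holds for section 7(f). It commits an unrandomized before-after pilot of three homes to inferential comparisons of intervention effect by sex, race and ethnicity, which the design cannot identify and section 3(d) does not plan. Such contrasts would also be imprecise: about ±0.56 SD of change for women vs men and ±0.77 SD for White vs Black residents, at 57 residents in section 7(f)'s proportions, assuming independent residents and no missing data. The identification problem does not shrink with sample size; how large the bias would be is unknown.

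The design label in sections 9(b) and 12 is a minor inconsistency. It should be corrected because it is wrong and because one instance describes the consent discussion, but it changes nothing in the conduct or analysis of the pilot.

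**What to change.** **Section 7(f).** Limit the pilot to descriptive summaries of the section 3(d) kind: pre-post change by sex and by race/ethnicity, labelled as change and not as intervention effect. State that comparisons of intervention effect are reserved for the R33.

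**Sections 9(b) and 12 item 2.** Replace the design sentence with: this is an unrandomized pilot (R61) in which each NH serves as its own control, testing methods for a subsequent stepped-wedge cluster randomized trial (R33). Section 8(a) item 7 should not be copied word for word, because it puts the own-control property inside the parenthesis describing the R33, whereas section 2(c) also gives it to the pilot. Check that the consent discussion matches.

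**Cost.** Three text edits and one check of consent wording. Data collection, sample size and the analyses in section 3(d) do not change.
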